The Virtual Reality Insertion of Chest-drain Outcomes Research (VICTOR) study will compare the traditional teaching of chest drain insertion against an immersive Virtual Reality (VR) training system. Junior and senior anaesthetic registrars will be the targeted study population and will be randomly assigned to one of the two study groups. The traditional education group will receive instruction on chest drain insertion via written text and an instructional video. The VR education group will receive instruction via the VR software training programme. After instruction, both groups will be assessed by two blinded researchers using a validated chest drain insertion assessment tool.

Assessment of chest drain insertion will be done by utilizing a simulation mannikin fitted with a chest drain insertion module. Any differences between the traditional training group and the VR group will be assessed by measuring the following outcomes; Scores recorded on a validated checklist for chest drain insertion proficiently, time to completion of the task and the number of deviations from the checklist. Self-reported participant confidence will also be recorded.

2 Rationale / Background

Virtual reality is a computer-generated 3D virtual environment. This virtual environment can be defined as one that "capitalizes upon natural aspects of human perception by extending visual information in three spatial dimensions", "may supplement this information with other stimuli and temporal changes" and "enables the user to interact with the displayed data (1)." The ability to create virtual worlds that the user can then interact with makes VR a potentially useful simulation-based education tool.

Due to the multitude of terms used to describe virtual reality education (VRE) the following table has been included. The included table (2) provides specific definitions for terms related to VRE.

Table 1: Standard definition of terms

Г

Virtual Simulation A screen-based simulation where the graphics, sound
--

	emphasize the 3D nature of the environment.	
Virtual Reality	Use of immersive, highly visual, 3D characteristics to replicate real-life situations; typically incorporates physical or other interfaces such as a head-mounted display, motion sensors, or haptic devices in addition to computer keyboard, mouse, speech, and voice recognition. The user interacts as if it takes place in the real world and the focus of the interaction remains in the digital environment.	
Augmented Reality	A type of VR in which synthetic stimuli are superimposed on real-world objects (overlays digital computer-generated information on objects or places in the real world) for the purpose of enhancing the user experience; may include head-mounted display, overlays of computer screens, wearable computers, or displays projected onto humans and mannequins. The focus of the interaction of the performed task lies within the real world instead of the digital environment.	
Virtual Standardised Patient	Avatar-based representations of human standardized patients that can converse with learners using natural language	
Serious Games	Interactive computer applications simulating real-world events designed for a primary educational purpose rather than pure entertainment. Present challenging goals; are engaging to the user; incorporate some scoring mechanism; and supply the user with skills, knowledge, or attitudes useful in reality	

The VRE in this study will fall under the definition for virtual reality, as it incorporates a head mounted display (oculus rift headset) to create an immersive virtual world.

Simulation based education (SBE), with deliberate practice as a teaching tool, has been shown to be superior to traditional clinical education for acquisition of a wide range of medical skills.(3) With the recent technological advances in virtual reality hardware in terms of graphic ability, portability and cost, there is increasing interest in the use of VR in SBE. The traditional Halsted's educational model of *"see one, do one, teach one"* has held a prominent place in the teaching of all surgical specialities (4). The same educational model has been applied by other medical disciplines, but it is insufficient in terms of patient safety with trainees learning by practising on real patients (5). SBE does not expose patients to avoidable and preventable errors (6) and thus may improve patient safety and comfort.

Virtual reality technology has previously been used by various medical disciplines, as an educational tool. The majority of VR use has been in the areas of surgical, gynaecological and gastrointestinal procedural training (4, 7). There are currently very few studies looking at task based virtual reality training in anaesthesia.

There are a number of advantages in the use of VRE and these include; repeatability, portability, selfdirected learning, data collection, and cost (8). Taekman et al attribute further human elements such as, instant feedback, rewards, competition, scalability, standardisation and convenience (9).

Virtual Reality Education provides an opportunity to deliberately practise rare, potentially lifesaving procedures and scenarios in a risk-free environment. These advantages make VRE an attractive educational tool, provided that the virtual reality education program is at least as effective or superior to the traditional education method. This remains the motivation behind this pilot study.

3 **Project Aims / Objectives / Hypotheses**

Primary objectives: Compare the effectiveness of VRE training with traditional education methods for the placement of a chest drain by anaesthesia registrars. Effectiveness of education will be assessed by proficiency of chest drain insertion, non-deviation from standardised chest drain checklist and the time taken to complete the task of chest drain insertion.

Secondary Objectives: Assessment of registrar levels of confidence regarding chest drain insertion pre- and post-educational sessions.

Hypothesis: VRE training is as effective if not superior to a traditional teaching approach for the insertion of chest drains.

Null Hypothesis: There is no difference in chest drain insertions outcomes when instructed by either a traditional or VR training approach.

4 Project Design

Project Design

Pilot study

Pre-test survey assessing prior chest drain insertion training; number of chest drain insertions performed in patients; current confidence level related to chest drain insertion ability.

Subjects randomly assigned to one of two groups

Traditional teaching method. Text and instructional video Virtual reality training method

All study participants will be assessed by two anaesthetic consultants blinded to group allocation using a validated checklist for chest drain competency. Chest drain insertion success with be assessed using scores from assessment tool, number of deviations from the checklist, time to task completion and self-reported chest drain insertion confidence levels.

Source and Selection of Participants

The study participants will be the junior and senior anaesthetic registrars from the Fiona Stanley & Fremantle Hospital Group Department of Anaesthesia & Pain Medicine. An email will be sent by [name] containing information regarding the study and a request for participation.

Participant inclusion criteria.

All the registrars in the Fiona Stanley & Fremantle Hospital Group Department of Anaesthesia & Pain Medicine as of 3rd August 2020.

Participant exclusion criteria.

Unwilling to participate or sign consent.

Not completing the chest drain training.

Adverse reaction to virtual reality hardware.

Previous use of the VR chest drain scenario if allocated to the control group.

Participant withdrawal criteria

If unable to use the virtual reality training program due to motion sickness, nausea or headache. The facilitators will attempt to improve the comfort of the headset. If the participant still cannot use the headset due to discomfort they will be removed from the study.

Bias

The participants will be allocated to groups by computer-generated randomisation. The assessors of the two groups will be blinded to the training method that all the participants received.

Blinding and Randomisation

Due to the varying skills/capabilities of the junior and senior registrars, the two groups will be randomised separately to ensure an equal balance between the control and experiment groups.

The researchers will have a separate list of participants that will contain the information regarding which training method each participant received. This will be correlated against the score sheets from the blinded assessors.

Method

The traditional education group will use the teaching material from the Emergency Trauma Management (ETM) course manual. This course is accredited as part of the professional development program by the Australian College of Rural and Remote Medicine. The VR education group will use the novel VR training software. Assessment of the two groups will be performed on a SimMan 3g mannikin with a chest drain module inserted. The assessment tool used is a validated checklist for chest drain insertion proficiency.

Project Duration/Schedule

The expected duration of data collection is six months. Data analysis is expected to take a further 6 months to complete. This includes the writing of a research manuscript for publication.

Project Termination

Once all participants have completed their allocated training program and have been subsequently assessed by a blinded assessor the data collection process will end.

5 Treatment of Participants

Description and justification for treatments, interventions or methods to be utilised

The hypothesis that the VRE may prove to be a more effective training method is of potential benefit to all the study participants and patients, especially as this technology becomes more widely incorporated into medical training. The *"Traditionally trained"* group will not be disadvantaged as this is currently the accepted standard of training. Furthermore, access to the VR training software will be made freely available to all participants once their blinded assessment has been completed.

Permitted medications/treatments

There is no medication or treatment in this study.

Monitoring of participant compliance

Onsite facilitators will be present to conduct the virtual reality training session. Facilitators will further ensure that the traditional group reads the notes provided and watches the instructional video.

6 Assessment of Efficacy

Outcomes

Raw scores on the validated chest drain insertion competency checklist

Any deviation from the validated checklist

Time taken for task completion

Matched confidence scores using Likert data from a pre- and post-intervention survey.

Efficacy assessment

The TACTIC validated checklist for chest drain insertion competency will be used (10). The assessors will determine the number of deviations from the checklist and record the time taken to complete the procedure. Confidence levels will be assessed via matched Likert data.

7 Assessment of Safety

Risks and Benefits

Potential risks to the participants include motion sickness, nausea and headaches from the virtual reality training programme. Facilitators will attempt to improve comfort and ensure correct use of the virtual reality headsets in order to limit these effects. Infection risk and cross contamination will be managed by the use of a UVC irradiation device.

Emergent chest drain insertion is a potentially life-saving procedure and the benefits for potentially improving knowledge and skill of chest drain insertion is enormous.

Safety

Facilitators will be present and monitor for any ill effects developing as a result of the training intervention. Infection control will be provided via UVC irradiation device, used on the virtual reality headset. The controllers will be wiped down with disinfectant wipes between uses.

Adverse events reporting

Any adverse events will be reported via the research team.

- Minor event: follow up with candidate
- More serious event: Regular follow up until resolved/ referral to care provider as determined by independent assessment.

Follow-up of Adverse Events

Any adverse events will be followed up until resolution of any symptoms.

8 Data Management, Statistical Analysis and Record Keeping

Statistics and Interim Analysis

Wilcoxon signed-rank test will be employed to assess any differences that may exist between the two groups. Likert-type questions will be used to obtain self-reported confidence data pre- and post-educational sessions. The median results of the Likert-type questions will be shown to describe central tendency.

Sample Size

The pilot project will use a convenience sample of Anaesthesia registrars at FSFHG. Currently there are 51 registrars. All registrars will be approached to participate. The study is a proof of concept study. Due to the fact that virtual reality software has only recently been developed, there is to the best of our knowledge no other published data to refer to. If a difference is noted between the study groups, a power analysis will be conducted to calculate the sample size necessary in a follow up study, to confirm differences that may exist.

Study Power and Significance

A validated checklist will be used to assess each candidate's placement of a chest drain. This checklist has 20 steps, graded out of 40 points, that must be completed in order for the chest drain placement to be deemed safe & successful. The mean score of the two study groups will be compared. A difference in the mean score p value of 0,05 will be deemed significant.

A power analysis will be conducted for a subsequent study, based on the results of this pilot trial.

As there is no data for VR teaching in terms of medical procedures in anaesthesia this study will provide a baseline comparison to traditional teaching. Certainly, an increase of 20% in the mean score would be seen as significant.

Statistical plan deviations

There is no anticipated deviation from the scoring system used to assess the placement of the chest drain. Incomplete scoring systems will not be included in the final analysis but may be used to make trends in comparisons between the two groups. Should any unanticipated protocol deviation occur this will be reported to the hospital ethics committee and a decision to proceed further will be made by the investigators.

Selection of participants for analyses

Participant selection will be via a convenience sampling of Anaesthesia Registrars from the Department of Anaesthesia and Pain Medicine at FSFHG. All consenting and participating registrars will be included in the final analysis of the two teaching methods employed in the study.

Data Management

All of the participate data will be anonymised and deidentified. The data will be stored on the chief investigator's password protected work computer. The data will only be accessible by the research team. The computer is locked in a cupboard in the anaesthetic department, which is only accessible by staff access security badges. Access to this data will be further blocked by passwords to specific folders minimizing access. No personal data will be shared with any 3rd party sponsors or external teams. Data including electronic, hardcopy and consents will be stored for a period of 7 years from the period of publication and will be made available should a written request be made by the ethics committee or hospital board. The data, hardcopies and consents will be destroyed after 7 years.

Procedure for accounting for missing, unused, and spurious (false) data.

All collected data will be analysed by each member of the investigating team. Incomplete data will not be included in the final analysis. Incomplete data may be used to analyse trends in the data from which no final conclusions will be drawn. Incorrectly completed checklists will not be utilised for final analysis.

9 Monitoring / Audit

Monitoring, Audit and Regulatory Inspections Statement

The project investigators/institutions will permit project-related monitoring, audits, and regulatory inspections, providing direct access to source data/documents. This may include, but not limited to, review by external sponsors, Human Research Ethics Committees and institutional governance review bodies.

Procedures for Monitoring and auditing

The project investigators will allow for any monitoring of processes to occur during the investigation. Further nomination by FSFHG Innovation Group or Vantari in terms of requests for monitoring will be considered by the investigating group.

10 Quality Control and Quality Assurance

Compliance statement

The project will be conducted in compliance with the protocol, Good Clinical Practice and the application regulatory requirements.

Quality control

Quality control & quality assurance measures to ensure quality of data.

11 Ethics

In terms of the ethical considerations related to "Research merit and integrity" the research is believed to be justifiable through the potential benefit of improved training and patient safety. The study has been designed using appropriate methods to achieve the aims outlined in the proposal. This is novel research, medical VR software has only recently been created and our research team is the first to study its application. The study has been designed to ensure that respect for the participants is not compromised by the aims of the research, its methodology, or results. The study will be conducted and supervised by appropriately trained and qualified persons or teams. The study will be conducted using appropriate facilities and resources. Participant integrity will be ensured by conducting the research under the over-riding principles of Good Clinical Practice, a commitment to searching for knowledge and understanding; following recognised principles of research conduct; conducting research honestly; and disseminating and communicating results, whether favourable or unfavourable, in ways that permit scrutiny and contribute to public knowledge and understanding.

In terms of "Justice" the researchers will take into account the scope and objectives of the proposed research. The selection, exclusion and inclusion of categories of research participants will be fair and accurately described in the results of the research. The process of participant recruitment will be fair; there is no unfair burden of participation in research for any particular group. There is a fair distribution of the benefits of participation in research and there is no exploitation of participants in the conduct of research. We will ensure that there is fair access to the benefits demonstrated through the results of the of research. Research outcomes will be made accessible to all research participants in timely and clear manner.

In terms of "Beneficence", the possible benefits of the study outweigh any potential risks to the participants. The study has been designed to minimise any risks of harm or discomfort that may be experience by any participant. The potential benefits and risks will be clearly explained to all participants in the consent document.

In terms of "Respect", the participants will be recognised for their intrinsic value. This recognition will be demonstrated through the values of research merit and integrity, justice and beneficence. The study will respect and acknowledge the welfare, beliefs, perceptions, customs and cultural heritage, both individual and collective, of those involved in research. The research group will respect the privacy, confidentiality and cultural sensitivities of all the participants. Respect for the participants will be maintained by supporting autonomy throughout the research procedures.

The consent form was created using guidance from the National Health and Medical Research Council.

12 Budget, Financing, Indemnity and Insurance

The innovation group of the Fiona Stanley & Fremantle Hospital Group has provided \$7919 for a virtual reality ready laptop computer and UVC irradiation hardware for infection control. Vantari VR is providing the VR software free of charge. The traditional group's learning materials have been provided free of charge from the Emergency Trauma Management course.

13 Publication

Publication in a high impact international anaesthetic journal.

14 References

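### The hypothesis includes equal effectiveness, but the only planned rule is a difference test at 0.05 with no margin, so a non-significant result could be misread as support for it

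*Protocol*

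**What the plan says.** Protocol section 3 (Project Aims / Objectives / Hypotheses) gives the hypothesis as "Hypothesis: VRE training is as effective if not superior to a traditional teaching approach for the insertion of chest drains". Directly beneath it stands "Null Hypothesis: There is no difference in chest drain insertions outcomes when instructed by either a traditional or VR training approach". Section 2 (Rationale / Background) explains why the question matters: VR education is attractive "provided that the virtual reality education program is at least as effective or superior to the traditional education method", and this is named as the motivation for the pilot.

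Section 8 sets the decision rule. Under Statistics and Interim Analysis, "Wilcoxon signed-rank test will be employed to assess any differences that may exist between the two groups". Under Study Power and Significance, "A difference in the mean score p value of 0,05 will be deemed significant". The only effect size mentioned is in the same place: "Certainly, an increase of 20% in the mean score would be seen as significant". On the instrument: "This checklist has 20 steps, graded out of 40 points". On numbers, under Sample Size: "Currently there are 51 registrars". All are to be approached, as a convenience sample for a proof-of-concept study.

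The protocol contains no non-inferiority or equivalence margin, no confidence-interval criterion, and no statement of how a non-significant result will be interpreted.

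**The concern.** The hypothesis has two halves: VR is equal to traditional teaching, or VR is better. The stated null covers the first half entirely. A test of that null can reject it in VR's favour, which supports the second half, or against VR, which contradicts both. If it does not reject, nothing has been shown. No outcome of the planned test counts as positive evidence for the first half, although section 2 makes that half part of the reason for the study.

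What is at stake is the wording of the conclusion. A non-significant p-value would sit beside a hypothesis that it appears to satisfy. With at most 51 participants, that p-value is compatible with VR training being moderately worse.

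**Working it through.** **Is there a figure to reproduce?** No. The protocol states no power, SD or margin, and 51 is a headcount. The check therefore compares the logic of the passages and then illustrates the size.

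**Logic.** Let D be the mean checklist score under VR minus that under traditional teaching.

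- Section 3 hypothesis: D is about 0, or D > 0.
- Section 3 null: D = 0.
- Section 8 rule: call D different from 0 if p reaches 0.05.
- Needed to support 'as effective': evidence that D > -M for some stated M. The protocol gives no M.
- The 20% figure concerns an increase, so it is a benchmark for gain and not a tolerated loss. It cannot serve as M.

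**Inputs for the illustration.**

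- From the protocol: 51 registrars, the 40-point scale and the 0.05 level.
- Assumed: full participation, a 26/25 split, a two-sided test, and a two-sample t-test on the mean score. The signed-rank test named in section 8 is a paired procedure. Its fit to two independent groups is a separate matter and does not affect this point.
- Assumed: an SD of 4 to 6 points wherever results are given in points.

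**Precision.** Standard error in SD units = sqrt(1/26 + 1/25) = sqrt(0.03846 + 0.04000) = 0.2801. With 49 degrees of freedom, t(0.975) = 2.0096. The 95% CI half-width is 2.0096 × 0.2801 = 0.563 SD. In points this is 0.563 × 4 = 2.25 to 0.563 × 6 = 3.38, or about 2.3 to 3.4 of 40.

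**Chance that a true loss is non-significant.** Noncentrality = loss in SD / 0.2801. The probability is that a noncentral t on 49 degrees of freedom falls between -2.0096 and 2.0096.

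| True VR loss | Noncentrality | P(non-significant) |
|---|---|---|
| 0.3 SD (1.2 to 1.8 points at SD 4 to 6) | 1.07 | 0.817 |
| 0.5 SD (2 to 3 points at SD 4 to 6) | 1.79 | 0.583 |
| 8 points at SD 6 (1.33 SD) | 4.76 | 0.003 |
| 8 points at SD 4 (2.0 SD) | 7.14 | below 0.001 |

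**Fewer participants.** Consent is voluntary, so 51 is the best case. With 40 (20/20) the first two probabilities become 0.85 and 0.66. With 30 (15/15) they become 0.88 and 0.74.

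**Dependence on the SD.** By normal approximation at 25/26, a true loss of 3 points is non-significant about 5% of the time at an assumed SD of 3 (power 0.946), 43% at SD 5 (power 0.572) and 73% at SD 8 (power 0.267).

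**What a margin would demand.** For a non-inferiority comparison with true D = 0, one-sided 0.025 and 25/26 per group, power for assumed margins of 2, 3 and 4 points is 66%, 95% and above 99% at SD 3; 30%, 57% and 82% at SD 5; and 14%, 27% and 43% at SD 8. Whether this sample could support the claim depends wholly on two quantities that the protocol does not give.

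**The case against.** The strongest reply is that this is a pilot and should be read as one. The protocol calls it a proof-of-concept study in a convenience sample, intended as a baseline comparison, with any difference to be taken to a later sample-size calculation. The primary objective in section 3 is neutral, since it only compares effectiveness. Section 5 presents the hypothesis as VR possibly proving the more effective method, and the 20% benchmark is a gain. On that reading the design is a difference test with one loosely worded sentence. Much of this stands. It lowers the severity and argues against forcing a margin where, by the protocol's own account, no earlier data exist. It does not remove the mismatch, because section 8 attaches a 0.05 rule to the comparison and section 2 makes the at-least-equal question part of the motivation.

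Two stronger readings are tempting, and the documents support neither.

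- A reader might infer that the investigators plan to present a non-significant result as equal effectiveness. The protocol never says so. It could be misread that way, but no such conclusion is planned.
- A reader might infer that a clearly worse VR programme would often go undetected. That depends on what counts as clearly worse and on an SD that is not given. If the 20% benchmark is read as 8 of 40 points and turned into a loss, a loss of that size would be missed less than 0.4% of the time at SD 4 to 6. If it is read relative to an assumed control mean of 20 to 30 (4 to 6 points), the range is about 0.05% to 35%.

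It might also be said that the statistical analysis plan could settle this. That plan is not shown, but the hypothesis, the null and the significance rule are all fixed in the protocol and do not match one another there.

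**Conclusion.** The point holds. The planned test can support superiority but cannot support equal effectiveness, and the protocol contains nothing else that could. At full enrolment, losses of 0.3 and 0.5 SD would be non-significant 82% and 58% of the time, and the 95% CI would extend 0.56 SD either side of the estimate. These figures rest on 26/25 participants and a two-sided t-test. Their translation into 2.3 to 3.4 points rests on an assumed SD of 4 to 6. Small to moderate losses could pass unnoticed, while very large ones would rarely do so. The difference comparison itself remains meaningful; the hypothesis claims more than the comparison can show. Severity: should-fix.

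**What to change.** In section 3, delete *as effective* and state a difference or superiority hypothesis that matches the existing null. In section 8, make the VR minus traditional difference in checklist score, with its 95% confidence interval, the main reported result. Add that a non-significant p-value is inconclusive and will not be presented as equal effectiveness.

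Only if the investigators wish to keep the equal-effectiveness claim should they set and justify a margin in checklist points before any scores are unblinded. They would then make the claim only if the lower limit of the 95% confidence interval lies above minus that margin.

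The cost is protocol wording, with no added participants, assessments or data. The drawback for the investigators is that a non-significant result can no longer be offered as support for the hypothesis.

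### Two rules remove randomised registrars according to their arm (prior VR use in control only, headset intolerance in VR only), which can bias the comparison by an unknown amount

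*Protocol*

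**What the plan says.** Section 4 fixes allocation by chance: "The participants will be allocated to groups by computer-generated randomisation". Because juniors and seniors differ in skill, "the two groups will be randomised separately to ensure an equal balance between the control and experiment groups".

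The exclusion criteria in the same section contain three entries that bear on this point:

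- "Previous use of the VR chest drain scenario if allocated to the control group"
- "Adverse reaction to virtual reality hardware"
- "Not completing the chest drain training"

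The withdrawal criteria cover registrars with motion sickness, nausea or headache. Facilitators first try to make the headset comfortable. After that: "If the participant still cannot use the headset due to discomfort they will be removed from the study".

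Section 8, under Selection of participants for analyses, says: "All consenting and participating registrars will be included in the final analysis of the two teaching methods employed in the study". Under the missing-data heading, the same section drops incomplete data from the final analysis. Nowhere does the protocol say that a removed registrar is still assessed on the mannikin or kept in the allocated arm.

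**The concern.** Randomisation makes the two arms comparable only as long as who stays in does not depend on the arm. Two of these rules break that condition.

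The prior-use rule treats two registrars with the same earlier VR practice differently: one is deleted because allocation fell on control, the other is kept because it fell on VR. The headset rule deletes registrars for whom VR training did not work. Yet being unable to use the headset is itself a result about the effectiveness of VR training, which is what Section 3 sets out to compare.

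The stake goes beyond this pilot's p value. Section 8 plans to size a follow-up study from these results, so an inflated difference would carry forward into too small a sample. With at most 51 registrars, a few removals matter. A later analysis plan cannot repair this, because it cannot recover scores from registrars who were never assessed.

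**Working it through.** **1. Which rules act after allocation, and on whom.** The protocol gives no removal rate, SD or dropout figure to reproduce, so the first step is to set the rules side by side.

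| Rule (Section 4) | When it can act | Arm affected |
|---|---|---|
| Unwilling or no consent | before randomisation | both |
| Prior use of the VR scenario | after allocation | control only |
| Headset cannot be used (withdrawal) | during training | VR only, as no earlier VR exposure is described |
| Training not completed | after allocation | both |
| Adverse reaction to VR hardware | unclear: entry history or in-study event | both, or VR only |

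The second and third rows are arm-linked on their face. The fourth is post-allocation but symmetric in wording.

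**2. Prior-use rule.** Let *q* be the share of prior users, equal in both arms through randomisation, and *g* their advantage in SD. The VR arm keeps them, so its mean is raised by *q* × *g*; control loses them, so its mean is not. The bias in favour of VR is therefore *q* × *g*. Both inputs are assumptions:

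- *q* = 5%, *g* = 0.25: 0.05 × 0.25 = 0.01 SD
- *q* = 10%, *g* = 0.5: 0.10 × 0.5 = 0.05 SD
- *q* = 20%, *g* = 0.8: 0.20 × 0.8 = 0.16 SD

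**3. Headset rule.** Inputs: 51 registrars (Section 8), split 25 VR and 26 control (assuming about 1:1 and full uptake); significance level 0.05 (Section 8), taken as two-sided; a two-sample t-test, because Section 8 compares mean scores; no true effect. The VR registrars lowest on a trait with correlation *r* to the score are removed. The values of *r* and the numbers removed are assumptions. Results from 20,000 simulated trials per row:

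| Removed from VR | *r* | Bias (SD) | Type I error |
|---|---|---|---|
| 0 | – | 0.00 | about 5% |
| 1 to 5 of 25 | 0 | 0.00 | about 5% |
| 1 of 25 | 0.3 / 0.5 | 0.03 / 0.04 | 5.0% / 5.4% |
| 2 of 25 | 0.3 / 0.5 | 0.05 / 0.07 | 5.3% / 6.0% |
| 3 of 25 | 0.3 / 0.5 | 0.07 / 0.11 | 5.5% / 6.9% |
| 5 of 25 | 0.3 / 0.5 | 0.10 / 0.17 | 6.1% / 9.1% |

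Repeat runs move the error rates by a few tenths of a percentage point (6.1% to 6.6% for 5 of 25 at *r* = 0.3).

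A large-sample formula agrees. Removing the lowest fraction *f* shifts the mean by *r* × φ(z_f) / (1 − *f*), where z_f is the *f* quantile of the standard normal and φ its density.

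- *f* = 2/25 = 0.08: φ = 0.149, and 0.149 / 0.92 = 0.162. Times 0.3 is 0.05; times 0.5 is 0.08.
- *f* = 5/25 = 0.20: φ = 0.280, and 0.280 / 0.80 = 0.350. Times 0.3 is 0.105; times 0.5 is 0.175. Both are slightly above the simulated values because 25 is a small arm.

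**4. What the simulation leaves out.** It assumes no true effect, so a registrar who misses the VR training loses nothing by it. If training does help, those who cannot use the headset would score lower for lack of it. Leaving them out then overstates what VR training achieves across all registrars assigned to it, even at *r* = 0.

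**The case against.** The strongest reply is that harm is possible but not shown. The withdrawal causes are motion sickness, nausea and headache, and nothing in the protocol links these to chest-drain skill. At zero correlation the bias is nil, and with one or two removals it is small even at 0.5. Prior use may also be rare, since the protocol calls the software novel and recently developed. The survey in Appendix 1 is not shown, so it may already ask about prior use, although Section 4 does not list it. All of this stands. It limits the claim to *can bias*, with size unknown. It does not make the rules symmetric.

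Four stronger readings are tempting, and the documents do not support them:

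- *Every exclusion differs by arm.* Non-completion applies to both arms, and Section 5 has facilitators overseeing both. The adverse-reaction entry can be read as a known history checked at entry.
- *Section 8 flatly contradicts Section 4.* Someone removed from the study may simply no longer count as participating, in which case the analysis set is completers. This is an ambiguity to reconcile. On that reading the selection remains.
- *Releasing the VR software contaminates the controls.* Section 5 says "access to the VR training software will be made freely available to all participants once their blinded assessment has been completed". Access follows each registrar's own assessment, so it does not itself create prior use. That colleagues still waiting would be exposed is conjecture.
- *The pilot label excuses it.* The study still tests at 0.05 and feeds a later sample-size calculation.

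**Conclusion.** The point holds in a limited form. The protocol fixes two removals that act after randomisation and depend on the arm: prior users of the scenario leave control only, and headset-intolerant registrars leave VR only. Non-completion is a third post-allocation removal, open to both arms. Following the plan as written can therefore distort the comparison.

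The direction depends on conditions. The prior-use rule favours VR if earlier practice improves scores. Headset removal favours VR if intolerance or poor engagement goes with lower scores, and in any case it leaves failures of the method out of the count. A reader might infer that the result is certainly biased towards VR; the documents give neither a removal rate nor a link between intolerance and skill, so that inference goes too far.

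Under the stated assumptions the headset rule costs nothing at zero correlation. At correlations of 0.3 to 0.5 it adds about 0.05 to 0.08 SD for 2 of 25 removed and 0.10 to 0.17 SD for 5 of 25, with type I error rising from 5% to at most about 9%. The prior-use rule could add 0.01 to 0.16 SD. It is worth correcting before enrolment because the remedy is cheap and lost assessments cannot be recovered.

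**What to change.** 1. Ask about prior use of the VR scenario before randomisation, for example in the pre-test survey, and apply the same exclusion whichever arm is later assigned.
2. Leave the handling of headset discomfort as it is, but still assess on the mannikin, if they agree, registrars in either arm who stop or do not complete training.
3. Make the main analysis all randomised registrars in their allocated arm, with completers only as a sensitivity analysis. Report intolerance and non-completion by arm.
4. Reconcile the exclusion and withdrawal criteria in Section 4 with the analysis set in Section 8, and say whether the adverse-reaction entry is an entry criterion or an in-study event.

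The cost is protocol wording, a few more mannikin assessments, possibly one or two fewer eligible registrars, and a VR estimate that may be slightly less favourable. The timing of VR access after assessment need not change on this ground.
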